9.6 Data Management

9.6.1 Data Processing

GSK Vaccines S.r.l. will receive at least twice a year progress reports of meningococcal capsular group B cases from PHE, specified as mentioned above.

Blinding

GSK Vaccines S.r.l. will receive pseudo-anonymised or aggregated data only from PHE.

Data linkage

Data linkage, e.g. between MenB cases and their vaccination status, will be taken care of by PHE.

9.6.2 Software and Hardware

Analyses will be done by PHE.

9.7 Data Analysis

If additional or different analyses are needed, they will be defined before first subject is enrolled.

9.7.1 Statistical Hypotheses

No hypothesis is tested. This study determines the impact on meningococcal disease and effectiveness of 4CMenB vaccination against MenB disease, after introduction of 4CMenB in the UK.

9.7.2 Analysis of Demographics and Baseline Characteristics

Descriptive statistics will be performed as appropriate using standard statistical methods. For continuous variables mean, standard deviation, median, Q1, Q3, minimum and maximum will be calculated overall. Frequency distributions (n, %) of categorical

variables will be summarized overall. To analyze baseline differences in patients characteristics the chi-square test (binary variables), Mantel-Haenszel test for trend (categorical variables) or linear regression models (continuous variables), will be used where appropriate statistical significance will be defined as a P-value less than 0.05, and 95% CI will be therefore calculated.

9.7.3 Statistical Methods

For each of the proposed study designs, the statistical methods are as follows:

1. Descriptive (no hypothesis testing):

This study will provide a summary of the epidemiology of all capsular groups of meningococcal disease, e.g. by vaccination status, age, setting and method. The method will be purely descriptive and summarise the observed number of *N. meningitidis* cases reported to PHE, stratified by variable of interest. More details are described above.

2. Analytical study:

Vaccine effectiveness (VE) is generally defined as the % reduction in the attack rate in vaccinated compared with unvaccinated children in the same birth cohorts. VE will be assessed by the screening method, or by a case-control method if the screening method cannot be used (for example, if appropriate coverage data cannot be determined).

a. Screening method:

For this method, the VE can be estimated using the formula below, where PCV is the proportion of cases that are vaccinated and PPV is the proportion population vaccinated (coverage):

$$VE = 1 - (\underline{PCV \times (1-PPV)})$$
$$((1-PCV) \times PPV)$$

The vaccine effectiveness estimate will be calculated along with the 95% confidence interval using the exact binomial distribution for the proportion of cases vaccinated in each of the study settings.

b. Case-control method:

In case-control studies, vaccine effectiveness is based on the odds ratio (OR) and is defined as: VE = 1 - OR

The vaccine effectiveness estimate will be calculated along with the 95% confidence interval using the standard errors from logistic regression.

If it is decided to pursue a case-control method, for instance if uptake information is difficult to obtain, the three controls for each case would as a minimum be matched on age (same month of birth if that is sufficient to define vaccine eligibility for infants) and sex.

As mentioned earlier, additional calculations can be considered to investigate the doseresponse relationships for each antigen in the vaccine (versus having at least one antigen, as described in the secondary objective).

As the number of cases due to other capsular groups is expected to be too small for analysis within the study period, at a later stage, outside the scope of this study protocol, it could be envisioned to evaluate both cross protection against other capsular groups and any capsule replacement after introduction of the vaccine.

Subgroup analyses

If sample size allows, stratified analyses may be performed.

Methods to control for confounding

For this study the screening method will be used, which is a relatively quick and easy way to assess vaccine effectiveness. The 'cost' of the simplicity is that no control for confounding is possible.

For the case-control method, odds ratios and 95% confidence intervals will be calculated by using a multivariate conditional logistic regression after matching by age, gender and calendar time (c-c ratio 1:3). Covariates will be included into the multivariate model if they are significantly (p<0.05) associated with meningitis and change the point estimate between 4CMenB vaccination and MenB disease at least 10%.

Stratified analyses will be conducted to estimate the effect by age, gender and in specific subgroups e.g. immunocompromised subjects, method of data collection (databases versus networks) and outcome (meningitis serotypes). For all analyses we will accept statistical significance at a p-value<0.05. Analyses will be performed by using the statistical software package SAS.

Methods to control for effect modification

In case of case-control method, Breslow-Day test for homogeneity of the odds ratios and inclusion of interaction term in the conditional logistic regression model will be used in order to investigate effect modification.

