9.1 Study Design

The proposed designs of the study are as follows:

- 1. Descriptive study (no hypothesis testing): summary of the epidemiology of meningococcal disease, by vaccination status, age, etc. This description would focus on the epidemiology not only of MenB, but, if possible, also include other capsular groups in order to evaluate both cross protection against meningococci with other capsular groups and any replacement that may occur after introduction of the vaccine.
- 2. Analyses for effectiveness of 4CMenB will be performed prospectively using the screening method (see a brief outline below). If the screening method is inapplicable then a case control method would be used. All these study designs have successfully been used to assess effectiveness of the MenC conjugate vaccine in England [Bose A et al., 2003], [Ramsay ME et al., 2001], [Trotter CL et al., 2004].
- 3. Similarly to other retrospective methods, the screening method is based on a comparison of the proportion vaccinated among the cases and the population. However, it differs from other methods in that control is achieved by external standardisation, using an estimate of vaccine coverage which is derived from sources external to the study [Farrington CP, 1993].

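### In the fallback case-control analysis, the p<0.05 condition on covariates can exclude a confounder that does shift vaccine effectiveness, and the rule tests against meningitis, which is not the study outcome

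*Protocol*

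**What the plan says.** The case-control design is a contingency. Protocol section 9.1 states: "If the screening method is inapplicable then a case control method would be used".

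For that design, section 9.7.3 (methods to control for confounding) sets two conditions joined by *and*. The first is in "Covariates will be included into the multivariate model if they are significantly (p<0.05) associated with meningitis and change the point estimate". The second requires the covariate to "change the point estimate between 4CMenB vaccination and MenB disease at least 10" per cent. The text does not say whether the first association is tested crudely or adjusted for vaccination.

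Section 9.3.2 gives the primary outcome as a confirmed group B case by culture and/or PCR from a normally sterile site (case definition A). Section 7 describes invasive disease as causing both meningitis and septicaemia.

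On the model, the same subsection says "odds ratios and 95% confidence intervals will be calculated by using a multivariate conditional logistic regression after matching by age, gender and calendar time", with three controls per case. The shorter case-control paragraph earlier in 9.7.3, repeated in the Abstract, says only that the interval uses "interval using the standard errors from logistic regression".

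**The concern.** A covariate confounds if leaving it out shifts the vaccination estimate. The 10% condition addresses that directly. The p<0.05 condition asks instead whether the covariate-disease association is detectable, which depends on how many cases there are. Because both must hold, a covariate that moves the estimate by more than 10% is still discarded when its own p-value is 0.05 or more, and the reported VE is then the confounded one.

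The two conditions also name different outcomes: meningitis in the first and MenB disease in the second. Read literally, the first would screen covariates against only part of the case series.

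At stake is residual bias in VE under the fallback, in a direction that depends on the confounder.

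**Working it through.** **Planned size.** Section 9.5 gives 284 cases and 852 controls for 90% exposure in controls and VE 60%. With an odds ratio (OR) of 0.40, exposure in cases is 0.36/0.46 = 0.7826. The standard error of ln OR is √[1/(284 × 0.7826 × 0.2174) + 1/(852 × 0.90 × 0.10)] = 0.184, so the 95% CI for VE is 42.7% to 72.1%. The lower limit is above 40%, as the plan states. The figure 284 itself is not reproduced exactly (224 or 264 by two standard variants), but it is conservative and not in dispute here.

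**A confounder that the rule can miss (assumed).** Prevalence 10%; vaccination 50% with it and 94% without; disease OR 0.6; true VE 60%. Coverage is 0.10 × 0.50 + 0.90 × 0.94 = 0.896, close to the plan's 90%.

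- Control proportions: with confounder, vaccinated 0.050 and unvaccinated 0.050; without, 0.846 and 0.054.
- Relative case weights (× 0.40 if vaccinated, × 0.6 if confounder present): 0.012, 0.030, 0.3384, 0.054.
- Unadjusted vaccination OR: (0.3504/0.0840) ÷ (0.896/0.104) = 4.171/8.615 = 0.484, so VE is 51.6%. The change is 0.484/0.400 = 1.21, or 21%, well over the 10% condition.
- Crude confounder-disease OR: (0.042/0.3924) ÷ (0.100/0.900) = 0.963. Lower vaccination masks the lower risk, so a crude test sees almost nothing.
- Adjusted test: ln 0.6 = −0.511. The simulated standard error is 0.267 at 284 cases and 0.444 at 107, so |z| is about 1.9 and 1.2. The expected 21% shift is the same at both sizes; only the p-value differs.

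**A confounder in the other direction (assumed).** As above with disease OR 1.5. Case weights are 0.030, 0.075, 0.3384 and 0.054. The unadjusted OR is (0.3684/0.129)/8.615 = 0.331, so VE is 66.9%. The crude confounder OR is (0.105/0.3924)/0.1111 = 2.41, which a crude test usually detects.

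**Simulation.** 3,000 unmatched 1:3 data sets per row, logistic model, Wald p-values, change measured as |OR crude/OR adjusted − 1| ≥ 0.10. Entries are the share of studies keeping the confounder, then median VE.

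| Disease OR | Cases | 10% rule alone | Joint, adjusted test | Joint, crude test |
|---|---|---|---|---|
| 0.6 | 284 | 84%, VE 60% | 49%, VE 57% | 3%, VE 52% |
| 0.6 | 107 | 75%, VE 59% | 20%, VE 54% | 3%, VE 51% |
| 1.5 | 284 | 79%, VE 61% | 45%, VE 63% | 79%, VE 61% |
| 2.0 | 284 | 99%, VE 60% | 90%, VE 60.5% | 99%, VE 60% |

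The plan does not set 107 cases for this scenario; that row only shows the dependence on size. For scale, Table 3 expects 164 cases at age 1 year over three years.

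**Milder confounders (assumed), in 1:3 matched sets.** Six scenarios were run, with prevalence 2–30%, disease OR 1.5–5 and vaccination OR 0.2–0.5. At 284 cases the joint rule and the 10% rule gave the same VE. At 73 cases they differed by at most 0.3 points.

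**The case against.** The strongest case against has four parts.

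- **Scope.** The rule applies only if coverage data fail. Section 9.7.3 says the planned screening method allows no control for confounding at all. This stands and limits the importance of the point.
- **Strength of the scenario.** Vaccination of 50% against 94% is an OR of (0.50/0.50)/(0.94/0.06) = 0.064, which is extreme. With milder confounders the extra condition costs almost nothing, and with disease OR 1.5 and a crude test it costs nothing at 284 cases. This stands: the loss is possible, not typical.
- **Covariate choice belongs in the SAP.** True of a covariate list. But the protocol states an explicit selection rule, and that rule is what is at issue.
- **Meningitis is a slip.** The same sentence goes on to name MenB disease, so few would be misled. Fair, but it is still the wrong outcome in a stated criterion.

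Two stronger readings are tempting. A reader might infer that the earlier paragraph plans an ordinary logistic regression that ignores the matching and so pulls VE towards zero. The documents do not support this: that paragraph leaves the type of logistic regression open, and the confounding subsection names conditional regression for both odds ratios and intervals. A reader might also infer that the "Breslow-Day test for homogeneity of the odds ratios" is to be applied across sets of one case and three controls. The text does not make the matched sets the strata. The stratified analyses listed just before it are by age, gender and subgroup, and the interaction term in the conditional model is already planned.

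**Conclusion.** The point holds as a defect in a stated rule, confined to the fallback design. The p<0.05 condition can discard a covariate that shifts the estimate by more than 10%, and the outcome it names does not match section 9.3.2.

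At 284 cases the effect ranges from none to a VE of about 57% (adjusted test) or 52% (crude test) against a true 60%. The 52% figure is a shift in ln OR of ln(0.48/0.40) = 0.18, about one standard error of the planned estimate. It rests on the assumed confounder with disease OR 0.6 and a large vaccination difference. Under the adjusted test the loss grows as cases fall. It would be too strong to say that VE stays confounded in most studies: that depends on confounder strength and on which test is meant, and neither is fixed by the document.

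**What to change.** In section 9.7.3:

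1. Delete the p<0.05 condition. Either pre-name a short list of covariates on subject-matter grounds, or keep the 10% change criterion alone. The latter still tolerates some bias: one covariate omitted for a change just under 10% leaves an OR of 0.40 between about 0.36 and 0.44 (VE 56% to 64%), and several could add up. Pre-naming avoids this.
2. Replace meningitis with case definition A.
3. As harmonisation only, write conditional logistic regression in the Abstract and in the case-control paragraph, as the confounding subsection already does.

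The cost is wording, plus slightly wider intervals when a non-confounder is kept. Section 9.7 asks for changed analyses to be defined before the first subject is enrolled, so the edit belongs before the fallback is invoked.

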isolate available from sterile site), but where a capsular group B isolate from a throat swab is available, MATS will be performed on the throat isolate instead.

GSK Vaccines will provide MATS kits to MRU.

If it is decided to pursue a case-control study instead of using the screening method, for instance if uptake information is difficult to obtain, three controls per case will be selected from the same population as where the cases arose from. This can for instance be from the same general practitioner's practice or local health economy, as where the case is registered in order to control for residential area. Three controls per case could be matched by age at the date the case occurred (date of month) and gender.

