Figure 6 Vaccination Status by Birth Cohort Over Time, UK

Potential situation at baseline: eligibility for vaccination in the first year of introduction of 4CMenB vaccine into the UK (e.g. from 1 January 2013):

Introduction of 4CMenB into NIP

From UK data presented at EMGM 2011, it is known that about 40% (5/12) of IMD cases below the age of one year occur in infants under 5 months of age. Taking into account that these children may not be well protected by the 4CMenB vaccine yet, the calculations use a VE of 0% at < 5 months of age. Similarly, for the ages 5 until 12 months of age, we assumed a slightly lower VE of 50%, while for all other ages the VE is assumed to be 60%.

GSK Vaccines S.r.l.		Observational Study Protocol V72_38OB
03 SEP 15 Version 3 Final	Confidential	Page 37 of 61

Potential situation after three years (e.g. at 31 December 2015): fully and partially (< 1 year of age) vaccinated birth cohorts:

Year 2013	1992	1993	1994	1995	1996	1997	1998	6661	2000	2001	2002	2003	2004	2005	2006	2007	2008	2009	2010	2011	2012	2013	2014	2015	
Year 2014	1992	1993	1994	1995	1996	1997	1998	1999	2000	2001	2002	2003	2004	2005	2006	2007	2008	2009	2010	2011	2012	2013	2014	2015	
Year 2015	1992	1993	1994	1995	1996	1997	1998	1999	2000	2001	2002	2003	2004	2005	2006	2007	2008	2009	2010	2011	2012	2013	2014	2015	

Fully vaccinated birth cohort

Partially vaccinated birth cohort

OBS-01 TEMP 01 / Atlas No. 295927 Version No. 2 / Version Date: March 30, 2015

┢

GSK Vaccines S.r.l.		Observational Study Protocol V72_38OB
03 SEP 15 Version 3 Final	Confidential	Page 38 of 61

From this schedule, using observed numbers of cases in the epidemiological year 1 July 2009 until 30 June 2010, the expected number of MenB cases for three years (2013, 2014 and 2015) has been calculated. Table 3 shows the expected numbers of meningococcal B cases after 4CMenB vaccination among infants and children in the United Kingdom assuming vaccine effectiveness of 60% and vaccine coverage of 90%.

Example: assuming a coverage of 90% (with 10% for unvaccinated) and VE of 60% in fully vaccinated infants between 12 and 24 months of age that currently have an observed number of 119 cases per year: (119*10%)+(119*90%*40%) = 55 expected cases per year. This age group is shaded in grey as an example in Table 3.

Table 3Observed and Expected Laboratory Confirmed Meningococcal
Capsular Group B Cases by Age and Epidemiological Year,
England & Wales, 2009-2010***

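### Breslow-Day is planned beside the conditional interaction term for the 1:3 matched fallback design; it ignores the matching and can mislead about VE by age

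*Protocol*

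**What the plan says.** Protocol section 9.7.3 makes the screening method the main analysis and keeps a case-control study in reserve. For that study VE is 1 minus the odds ratio, estimated by "multivariate conditional logistic regression after matching by age, gender and calendar time (c-c ratio 1:3"). Age matching is to the "same month of birth if that is sufficient to define vaccine eligibility for infants". Section 9.4 adds optional matching on place: "This can for instance be from the same general practitioner's practice or local health economy".

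Under the heading on confounding, section 9.7.3 says: "Stratified analyses will be conducted to estimate the effect by age, gender and in specific subgroups". It sets p<0.05 as the criterion for every analysis. Under the heading on effect modification it names two tools for the case-control design: "In case of case-control method, Breslow-Day test for homogeneity of the odds ratios and inclusion of interaction term in the conditional logistic regression model". It does not say on which tables Breslow-Day would be computed, or which of the two results decides.

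**The concern.** Breslow-Day tests whether odds ratios are equal across independent, unmatched 2x2 tables with adequate counts. Applied to one table per age band or per sex, it breaks the matched sets and compares crude odds ratios, whereas the protocol's VE is the matched one. Pooling matched sets pulls the crude odds ratio towards 1 when the probability of vaccination differs between sets. If that happens more in one band than in the other, the crude odds ratios differ although the matched ones do not.

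The protocol gives grounds to expect this in young children. Section 9.3.1 anticipates doses at 2, 4 and 12 months. Section 9.4.2 counts full routine vaccination from 14 days after the third injection. Section 9.7.3 itself links month of birth to eligibility. Age is also the modifier of most interest: section 9.5 assumes VE of 50% at 5 to 12 months and 60% at older ages, and it looks for conclusions in each age group. At stake is a report that VE is lower in the youngest vaccinated children when it is not, or silence about a real difference.

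**Working it through.** The plan states no figure for these tests, so there is none to reproduce.

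**Inputs from the Protocol (section 9.5):** 284 cases and 852 controls (1:3), 90% vaccination in controls, VE 60% (OR 0.4), alpha 0.05 (section 9.7.3).

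**Assumptions:** two age bands of 142 sets each, and the spread of vaccination probability between sets.

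**Formulas.** In a set with vaccination probability p, a case is vaccinated with probability p·OR/(1 − p + p·OR). The crude odds ratio of a band follows from the averages of p (controls) and of this quantity (cases).

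1. *Flat 90%.* Cases: 0.36/0.46 = 0.7826. Crude OR = (0.7826/0.2174)/(0.9/0.1) = 0.40, so crude VE is 60%. There is no distortion.
2. *Ages 12-23 months, nobody fully vaccinated in the first month, 90% afterwards.* Controls: 11/12 × 0.9 = 0.825. Cases: 11/12 × 0.7826 = 0.7174. Crude OR = (0.7174/0.2826)/(0.825/0.175) = 0.54, so crude VE is 46% although the true value is 60%.
3. *Roll-out ramp of 10, 40, 70, 85, 90, 90, 90, 90% by month.* Controls: 5.65/8 = 0.706. Cases: (0.043 + 0.211 + 0.483 + 0.694 + 4 × 0.783)/8 = 0.570. Crude OR = (0.570/0.430)/(0.706/0.294) = 0.55, so crude VE is 45%.

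**Simulation, true VE 60% in both bands** (Breslow-Day on the two age tables; likelihood-ratio test of the age-by-vaccination interaction in the conditional model). The other band is at a constant 90% unless stated.

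| Coverage between sets | Breslow-Day rejects |
|---|---|
| Flat 90% in both bands | 5.6% |
| Equal spread in both, SD 0.10 / 0.15 / 0.20 | 3.7% / 2.7% / 0.8% |
| Spread in one band only, SD 0.05 / 0.10 / 0.15 | 5.0% / 5.8% / 8.8% |
| Spread in one band only, SD 0.20 / 0.25 | 17.1% / 34.7% |
| Mild ramp in one band (60 to 92%) | 5.4% |
| Ages 12-23 months, ramps after the booster, including case 2 | 11-13% |
| Ramp of case 3 in one band | 14.7% |

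The conditional interaction test rejected about 4-7% of the time throughout. At a mean of 0.9 the largest possible SD is √(0.9 × 0.1) = 0.30, so the rows with SD 0.20 and 0.25 are close to all-or-nothing coverage.

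**Simulation, real difference (power, Breslow-Day versus conditional interaction):**
- VE 40% versus 70%: 46% versus 46% with no spread; 33% versus 39% with SD 0.10 in both bands; 7% versus 23% with SD 0.20 in both; 12% versus 45% with the ramp of case 3 in the high-VE band only.
- VE 80% versus 50%, assumed ramp at 12-23 months in the high-VE band: about 30% versus 70%.
- VE 50% versus 60%, as assumed in section 9.5: 9% versus 9% with no spread.

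**The case against.** The strongest reply is that the sentence in question already contains a valid test. The interaction term in the conditional model respects the matching, and nothing gives Breslow-Day priority over it. The design is a fallback, section 9.7.1 says that no hypothesis is tested, and at the protocol's own VE of 50% versus 60% neither test has useful power. All of this stands and keeps the point small. It does not justify keeping a test that answers a different question, and with no rule for disagreement a p-value below 0.05 from either test could be reported as effect modification.

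A reader might infer more than the documents support, in three ways.

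- *That Breslow-Day finds false age differences as a rule.* It does so only when coverage varies strongly between sets, and more in one band than in the other. With flat coverage it is nominal; with marked equal spread it is conservative. The documents give no figure for this spread.
- *That false rejection is near 50%.* Section 9.5 states that "about 40% (5/12) of IMD cases below the age of one year occur in infants under 5 months of age". If 5/12 of infant sets are taken as unvaccinated and the rest as 90% vaccinated, control exposure is 7/12 × 0.9 = 0.525, case exposure is 7/12 × 0.7826 = 0.457, crude VE is 24%, and Breslow-Day rejects in about 48-53% of runs. But 5/12 of those sets contain nobody who could be fully vaccinated. They carry no information on VE, section 9.5 sets VE to 0% at that age, and section 9.4.2 restricts the analyses to full, timely vaccination. Without these sets the scenario is flat coverage at about 5%.
- *That the test nearly always rejects.* Using each matched set as a stratum gives 99-100% rejection under the null (informative sets only), because four persons per stratum are too few. The protocol does not propose this, and it would not be a test by age.

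**Conclusion.** The concern holds in a limited form. Section 9.7.3 names a test that does not fit the matched design it prescribes, with no rule to put it second to the one that does. This is a stated method that fits badly, and not a detail left to an analysis plan. False rejection at a nominal 5% is about 5% with flat coverage, about 1-4% with marked equal spread, and about 11-15% with moderate ramps in one age band. It goes higher only when coverage in one band is close to all-or-nothing, as when many sets that cannot be fully exposed are pooled in. The loss of power ranges from none to large. These sizes rest on the assumed ramps and the 142:142 split. The direction of the bias does not: pooling sets with unequal coverage moves a crude odds ratio towards 1. The point is minor, because it matters only if the fallback is used and the primary VE estimate is unaffected.

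**What to change.** In section 9.7.3, under effect modification, delete the Breslow-Day test for the matched case-control design. State that effect modification is assessed only by the likelihood-ratio test of the vaccination-by-modifier interaction in the conditional logistic model. Report stratum-specific matched odds ratios (and VE) with 95% confidence intervals from that model. The interaction remains estimable for matching factors such as age and gender, although their main effects drop out. Breslow-Day would be suitable only if an unmatched design were adopted.

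The cost is one sentence. The replacement test is already planned, and no data or subjects are added.
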